1.4 POTENTIAL RISKS AND BENEFITS

The use of a replacement FIX product with a longer half-life and better recovery rate than currently available products should enable a longer interval between infusions for patients with hemophilia B. By reducing the burden on patients and physicians treating this disorder, such a product may also result in an improvement in patient compliance. In addition, it may permit primary prophylaxis in some young children without requiring the insertion of a venous access device.

Potential risks associated with rIX-FP are expected to be similar to the currently marketed recombinant FIX products and include the development of antibodies against FIX and development of thromboembolic complications. In addition, there is a risk of development of albumin and CHO cell-derived protein antibodies. The potential risks associated with treatment with rIX-FP are discussed in detail in Section 7.4 of the Investigator's Brochure.

The results from the rIX-FP nonclinical program and the data from previous clinical studies, support the evaluation of an rIX-FP treatment interval of between 7 and 14 days. The safety and efficacy of rIX-FP (100 IU/kg) using a 21-day treatment interval will also be examined in this study. Given that nonclinical studies in rats and cynomolgus monkeys have shown a no observed adverse effect level of 500 IU/kg, there is not expected to be any additional safety concerns regarding the use of rIX-FP at a dose of 100 IU/kg. There is a risk that administration of rIX-FP at a treatment interval of 21 days might be less effective at preventing bleeds than when administered at a treatment interval of 14 days or less. However, the PK evaluation of rIX-FP at a dose of 100 IU/kg will provide information on the trough FIX activity level using this dose of rIX-FP. In addition, prophylaxis treatment using a 21-day treatment interval will only be available to subjects \geq 18 years of age and who have completed at least 6 months of prophylaxis treatment with a 14-day treatment interval, with subjects in France excluded. If

Study Number: CSL654_3003
Study Product: rIX-FP

subjects do not benefit from a treatment interval of 21 days, they will be able to transfer to the 7-, 10-, or 14-day treatment interval at any time, at the discretion of the investigator.

This study will document all key safety factors including immunogenicity, thrombogenicity, hypersensitivity, and other AEs in the intended therapeutic population.

Thus, the associated benefit-risk assessment of the study is acceptable for subjects enrolled in the study.

2. STUDY OBJECTIVES AND ENDPOINTS

2.1 PRIMARY OBJECTIVE AND ENDPOINT

2.1.1 Primary Objective

The primary objective of this study is to evaluate the safety of rIX-FP as measured by new cases of inhibitors against FIX in subjects, including PUPs, with severe hemophilia B. The PK parameters in PUPs will also be collected.

2.1.2 Primary Endpoints

- The total number of subjects who develop inhibitors against FIX during the approximately 3-year participation in this study.
- PK parameter of incremental recovery (IU/dL per IU/kg) of 50 IU/kg rIX-FP (Arm 4 only).

2.2 SECONDARY OBJECTIVES AND ENDPOINTS

2.2.1 Secondary Objectives

The secondary objectives of the study are:

- To evaluate the efficacy of rIX-FP routine prophylaxis when administered at various treatment intervals.
- To compare the efficacy of rIX-FP routine prophylaxis between 2 different treatment intervals and versus on-demand treatment.
- To further evaluate the safety of rIX-FP.
- To evaluate the efficacy of treatment for bleeding episodes in PUPs.

2.2.2 Secondary Endpoints

- Annualized bleed rate (ABR) for spontaneous treated and total treated bleeds for each assigned treatment interval (7 days, 10 days, 14 days, and 21 days).

- Comparison of the annualized spontaneous bleeding rate (AsBR) and ABR between:
 - 14-day routine prophylactic treatment in this study compared with on-demand only treatment from Study CSL654_3001 Arm 2.
 - 7-day prophylaxis regimen with the 14-day prophylaxis regimen.
 - 7-day prophylaxis regimen with the extended prophylaxis regimen (10-day or 14-day).
- Consumption of rIX-FP during routine prophylaxis expressed as IU/kg per month per subject.
- Incidence of AEs and related AEs to rIX-FP over the course of the study.
- Hemostatic response to treatment of bleeding episodes with rIX-FP in PUPs as assessed by the investigator based on a 4-point scale (Arm 4 only).

CCI**CCI****CCI**

CCI

[figure not shown]

3. STUDY DESIGN

3.1 STUDY DESIGN AND RATIONALE

This is a multicenter, open-label, phase 3b study to investigate the long-term safety and efficacy of rIX-FP for the routine prophylaxis and on-demand treatment of bleeding episodes in subjects with hemophilia B. Subjects will be eligible to enter the study if they have completed studies CSL654_3001 or CSL654_3002, or any other CSL-sponsored rIX-FP (CSL654) study and meet all other eligibility criteria. In addition, subjects who have not previously completed a CSL-sponsored rIX-FP lead-in study may be eligible to enter the study if they require major non-emergency surgery and meet all other eligibility criteria, or if they are PUPs who meet the eligibility criteria.

Figure 1. Study Overview

1. Subjects from studies CSL654_3001 Arm 1, CSL654_3002, and subjects who have completed any other CSL-sponsored rIX-FP study are to participate in Arm 1 of the study.
2. Following the initial 6-month treatment period, all subjects may continue to use the same treatment interval, or change to 7, 10, or 14 days. Subjects ≥ 18 years of age, who have completed at least 6 months of prophylaxis treatment with a 14-day treatment interval, may also change to a 21-day treatment interval (not applicable for France). The treatment interval may be changed at each 6-month follow-up assessment or earlier if deemed medically necessary by the investigator. Subjects must undergo an initial pharmacokinetics evaluation with a single injection of rIX-FP (100 IU/kg) before starting treatment with a 21-day treatment interval for the first time (Subjects in France may not be assigned to a 21-day treatment regimen). Dose of rIX-FP administered for routine prophylaxis regimens is to be based on the subject's previous response to rIX-FP therapy and / or FIX trough activity. During routine prophylaxis therapy, subjects may also administer rIX-FP as on-demand (OD) therapy for bleeding episodes and may enroll in the surgery substudy (see [Appendix 1](#)) if they require a major or minor non-emergency surgical procedure.
3. Treatment interval (7, 10, or 14 days) for each subject to be determined by the investigator based on the treatment interval used in the lead-in study and / or investigator and subject preference.
4. All subjects who participated in Arm 2 of the CSL654_3001 lead-in study and who have < 26 weeks experience with a 7-day treatment interval at the start of this extension study are to continue a 7-day treatment interval for the first 6 months of the study or until they have accumulated ≥ 26 weeks experience with a 7-day treatment interval. At the end of this period, subjects in this group will be encouraged to switch to a 14-day treatment interval for a period of at least 6 months.
5. All subjects who participated in Arm 2 of the CSL654_3001 lead-in study and who have ≥ 26 weeks experience with a 7-day treatment interval at the start of this extension study are to start a 14-day treatment interval for the first 6 months of the study.
6. Subjects in Arm 3 (no subjects in France may participate in Arm 3) must undergo an initial rIX-FP pharmacokinetics evaluation before starting the surgery substudy. No subjects from France may enroll in Arm 3.
7. After completion of the surgery substudy, subjects may begin prophylaxis treatment with a 7-day treatment interval. Subjects in Arm 3 who require physical therapy (ie, rehabilitation after surgery), may administer rIX-FP as preventative treatment (no more than once per week) in addition to the administration of rIX-FP as routine prophylaxis. Preventative treatment before physical therapy is permitted only during the first 3 months of the treatment period.
8. Subjects in Arm 4 will administer rIX-FP as weekly prophylaxis and / or on-demand, prevention during the first 12 months, and then on weekly routine prophylaxis until completing 50 EDs. Subjects who complete 50 EDs are permitted to continue weekly routine prophylaxis with rIX-FP until the completion of the study..

3.1.1 Routine Prophylaxis: First 6 Months

Arm 1: Subjects from all lead-in studies (excluding CSL654_3001 Arm 2)

During the first 6 months, subjects in Arm 1 will administer rIX-FP as routine prophylaxis either using the same treatment interval as in the lead-in study or using a different treatment interval of 7, 10, or 14 days, as determined by the investigator. The dose of rIX-FP administered will be based on the subject's previous response to rIX-FP therapy and / or trough FIX activity (see [Section 6.2.1](#)) and dose guidelines in [Section 3.2.1.4](#) and [Table 1](#).

Arm 2

Subjects from lead-in Study CSL654_3001 Arm 2 who have ≥ 26 weeks experience with rIX-FP prophylaxis therapy with a 7-day treatment interval

During the first 6 months, subjects in this group will administer rIX-FP (75 IU/kg) as routine prophylaxis using a treatment interval of 14 days.

Subjects from lead-in Study CSL654_3001 Arm 2 who have < 26 weeks experience with prophylaxis rIX-FP therapy with a 7-day treatment interval

During the first 6 months, subjects in this group will administer rIX-FP as routine prophylaxis using a treatment interval of 7 days. The dose of rIX-FP administered will be the same as the dose used by the subject for routine prophylaxis in the lead-in study (see [Section 6.2.1](#)).

After a subject has accumulated at least 26 weeks experience with prophylaxis rIX-FP therapy (ie, lead-in study and current study combined), they may switch to a 14-day treatment interval or continue using a 7-day treatment interval until completion of the initial 6-month period. Subjects should attend an unscheduled visit and complete assessments as specified for the 6-month visit if they are to switch to a 14-day treatment interval before completion of the 6-month period. Under such circumstances, the 3-month visit may be omitted.

Arm 3 (Does not include any subjects in France)

Upon completion of the surgery substudy, subjects in Arm 3 may begin the prophylaxis treatment period in the main study. During the first 6 months, subjects will administer rIX-FP as prophylaxis using a treatment interval of 7 days. The dose (25 to 50 IU/kg) of rIX-FP administered will be based on the subject's trough FIX activity (see [Section 6.2.1](#)). During the first 3 months of the treatment period (ie, after surgery), subjects may also administer rIX-FP, no more than once per week, as a preventative treatment before physical therapy, if needed (see [Section 3.2.3](#)).

Arm 4

Subjects in Arm 4 will administer rIX-FP as weekly prophylaxis and / or on-demand, prevention during the first 12 months, and then on weekly routine prophylaxis until completing

50 EDs. Subjects who complete 50 EDs are permitted to continue weekly routine prophylaxis with rIX-FP until the completion of the study. The dose (25-50 IU/kg initially, up to 75 IU/kg) of rIX-FP administered will be based on the subject's clinical response, PK information or FIX trough activity.

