The dose of rIX-FP administered for routine prophylaxis will be based on the subject's previous experience (ie, in a lead-in study) and / or the targeted FIX activity trough level (target FIX activity level > 2%, but optimally between 5% and 15%). The maximum dose of rIX-FP for routine prophylaxis will be 50 IU/kg per injection for subjects using a 7-day treatment interval, 75 IU/kg per injection for subjects using a 10- or 14-day treatment interval, and 100 IU/kg per injection for subjects using a 21-day treatment interval. Subjects in France may not take part in the 21-day treatment regimen. The dose of rIX-FP for a subject using the 7-day treatment interval should not be higher than the dose they used in the lead-in study and / or a trough FIX activity of 20%.

On-demand Treatment

On-demand treatment with rIX-FP will be used for all bleeding episodes requiring treatment. The dose of rIX-FP (35 to 75 IU/kg) will be determined by the investigator, based on the effective on-demand treatment dose used in the lead-in study and / or the subject's PK data (determined in a lead-in study or Study CSL654_3003).

Prevention Before Vigorous Physical Activity or Physical Therapy

During the study, subjects may administer rIX-FP as a preventative treatment before vigorous physical activity or before physical therapy (ie, as a part of rehabilitation after major surgery) that, in the subject's experience, is likely to result in bleeding.

Preventative treatment before vigorous physical activity should not be used more frequently than **once per month**.

Preventative treatment before physical therapy (ie, after major surgery) should not be used more frequently than **once per week** during the first 3 months of either starting the prophylaxis treatment period (subjects in Arm 3, which excludes subjects in France) or returning to routine prophylaxis (subjects in Arms 1 or 2).

The dose of rIX-FP will be 35 to 50 IU/kg, as determined by the investigator and / or based on the subject's previous experience.

Subcutaneous Treatment in the Subcutaneous Substudy

Subjects will be sequentially assigned to a cohort, and receive a single SC dose of rIX-FP (in Cohorts 1 and 2) or repeated SC doses of rIX-FP (in Cohorts 3 and 4). The SC doses of rIX-FP will be administered at up to 4 injection sites, a minimum of 2.5 cm apart, with a volume of up to 4 mL per site. Subcutaneous administration may occur on the

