3.1.2 Routine Prophylaxis: 6 Months to End of Treatment Period

After completion of the initial 6-month treatment period, subjects from Arms 1, 2 and 3 will administer rIX-FP as routine prophylaxis using a treatment interval of 7, 10, or 14 days for the remainder of the study. Subjects from lead-in Study CSL654_3001 Arm 2, who were using a 7-day treatment interval during the previous 6 months, will switch to a 14-day treatment interval for at least 6 months.

From 6 months onwards, subjects (Arm 1, 2 and 3) may use the same treatment interval or they may change treatment interval in consultation with the investigator at any of the subsequent 6-month follow-up visits (see [Section 3.2.1.2](#)). For the first 12 months of the study, subjects in Arm 4 are encouraged, but not required, to be on weekly prophylaxis. The dose of rIX-FP administered will be between 35 and 75 IU/kg (see [Section 6.2.1](#)).

Subjects ≥ 18 years of age may also administer rIX-FP as routine prophylaxis using a 21-day treatment interval at a dose of 100 IU/kg. Subjects in France may NOT switch to a routine prophylaxis regimen using a 21-day treatment interval. Subjects < 18 years of age are not permitted to use a treatment interval of 21 days.

Subjects who transfer to a 21-day treatment interval for the first time must have completed at least 6 months of prophylaxis treatment with a 14-day treatment interval and have undergone PK evaluation with 100 IU/kg rIX-FP (see [Section 3.1.3](#)).

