3.2 DOSE AND DOSING REGIMEN

3.2.1 Routine Prophylaxis Treatment

3.2.1.1 *rIX-FP Treatment Interval*

During the first 6 months of the study, subjects or their caregivers will administer rIX-FP as routine prophylaxis using the following treatment intervals:

- Arm 1: 7, 10, or 14 days.
- Arm 2: 7 or 14 days.
- Arm 3: 7 days. (No subjects in France may participate in Arm 3)
- Arm 4: 7 days (preferred for the first 12 months of the study; required after the first 12 months of the study).

For subjects in Arm 1, the treatment interval will be chosen by the investigator at the beginning of the study based on the subject's previous experience (ie, during the lead-in study) and subject preference.

For subjects in Arm 2, the treatment interval will be based on the duration of their prophylaxis treatment in the lead-in study; a 14-day treatment interval will be assigned to subjects who completed at least 26 weeks of prophylaxis treatment during the lead-in study and a 7-day treatment interval will be assigned to subjects who did not complete at least 26 weeks of prophylaxis treatment during the lead-in study. Subjects in Arm 2 who start on a 7-day treatment interval and complete a total (ie, during the lead-in study and this study) of at least 26 weeks of prophylaxis treatment, should then switch to a 14-day treatment interval for a period of at least 6 months.

Upon completion of the surgery substudy, subjects in Arm 3 (not applicable to France) may begin the prophylaxis treatment period in the main study. During the first 6 months, subjects in this group will administer rIX-FP as routine prophylaxis using a treatment interval of 7 days. The dose (25 to 50 IU/kg) of rIX-FP administered will be based on the subject's trough FIX activity (see [Section 6.2.1](#)).

At the end of the initial 6-month period, subjects in Arm 1, 2 and 3 may remain on their current treatment interval or they may be switched to a 7, 10, or 14-day treatment interval. Subjects ≥ 18 years of age may also be switched to a 21-day treatment interval after completing at least 6 months of a 14-day prophylaxis regimen and a 100 IU/kg rIX-FP PK evaluation period (see [Section 3.1.3](#)). Subjects in France may NOT switch to a routine prophylaxis regimen using a 21-day treatment interval.

3.2.1.2 *Changing the rIX-FP Treatment interval (subjects in Arm 1, 2 and 3)*

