During each 6 months of the treatment period, the treatment interval *should not* be changed unless deemed necessary by the investigator for the subject's safety (with the exception of subjects from lead-in Study CSL654_3001 Arm 2 who have <26 weeks experience with prophylaxis rIX-FP therapy with a 7-day treatment interval). At the end of each 6-month period (ie, at the 6 month, 12 month, etc follow-up visits) the investigator may choose to change the treatment interval based on their assessment of efficacy / safety, subject treatment compliance, and / or subject preference.

3.2.1.3 *Changing the rIX-FP Treatment interval (subjects in Arm 4)*

During the first 12-month period, subjects in Arm 4 are encouraged, but not required to be on weekly prophylaxis regimen with rIX-FP. At the end of the initial 12-month period, subjects are required to be on a weekly prophylaxis regimen for rest of the study.

3.2.1.4 *rIX-FP Dose*

The dose of rIX-FP administered for routine prophylaxis will be based on the subject's previous experience (ie, during a lead-in study) and / or the targeted FIX activity trough level (target FIX activity level > 2%, but optimally, between 5% and 15%). The FIX activity trough level must not be targeted to $\geq 20\%$ without approval from CSL.

The maximum dose of rIX-FP for routine prophylaxis will be 50 IU/kg per injection for subjects using a 7-day treatment interval and 75 IU/kg per injection for subjects using a 10- or 14-day treatment interval ([Table 1](#)), unless a higher dose for a given subject is approved by

CSL. The dose of rIX-FP will be 100 IU/kg per injection for subjects using a 21-day treatment interval (Table 1). For all treatment intervals, the total dose of rIX-FP administered for routine prophylaxis over a 28-day period is not to exceed 250 IU/kg, without approval from CSL.

Table 1. Dose Guidelines for Routine Prophylaxis Treatment

| | Treatment interval | | | |
|------------------------|--------------------|----------------------|---------|---------|
| | 7 Days | 10 Days ¹ | 14 Days | 21 Days |
| Suggested dose (IU/kg) | 25 to 50 | 50 to 75 | 75 | 100 |
| Maximum dose (IU/kg) | 50 ² | 75 | 75 | 100 |

1. The 10-day treatment interval may be based on a schedule of once every 10 calendar days or 3 times a month (ie, 1st, 11th and 21st day of each month).

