2. An rIX-FP dose higher than 50 IU/kg is acceptable if the FIX activity trough level is < 5% at Day 7 and a higher trough level is necessary to prevent spontaneous bleeding.

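### The Arm 4 dose sentence allows up to 75 IU/kg weekly without the approval and trough conditions that the protocol attaches elsewhere to 7-day doses above 50 IU/kg

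*Protocol*

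**What the plan says.** **Interval.** Section 3.2.1.1 lists "Arm 4: 7 days (preferred for the first 12 months of the study; required after the first 12 months of the study". A prophylaxis patient in Arm 4 is therefore dosed every 7 days.

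**Section 3.1.1, Arm 4 paragraph (under the routine prophylaxis heading).** "Subjects in Arm 4 will administer rIX-FP as weekly prophylaxis and / or on-demand, prevention during the first 12 months, and then on weekly routine prophylaxis". The dose sentence comes next: "The dose (25-50 IU/kg initially, up to 75 IU/kg) of rIX-FP administered". It ties the choice of dose to how the child responds, to PK or to the trough. Neither sponsor approval nor Table 1 is mentioned. The Arm 1 text in the same section does point to Section 3.2.1.4 and Table 1.

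**Synopsis, prophylaxis treatment.** "The maximum dose of rIX-FP for routine prophylaxis will be 50 IU/kg per injection for subjects using a 7-day treatment interval". No exception is attached. This comes shortly after the synopsis text on Arm 4 weekly prophylaxis.

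**Section 3.2.1.4.** It gives the same 50 IU/kg maximum, but lets the sponsor approve more for an individual subject. It adds a second limit: "For all treatment intervals, the total dose of rIX-FP administered for routine prophylaxis over a 28-day period is not to exceed 250 IU/kg", again unless the sponsor approves. The section is not restricted to particular arms.

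**Table 1, footnote 2 (7-day column).** "An rIX-FP dose higher than 50 IU/kg is acceptable if the FIX activity trough level is" below 5% at Day 7 and a higher trough is needed to stop spontaneous bleeds. Approval is not mentioned.

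**Section 3.1.2.** "The dose of rIX-FP administered will be between 35 and 75 IU/kg", with a pointer to Section 6.2.1. The preceding sentence concerns Arm 4, but the section opens with Arms 1, 2 and 3.

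**The concern.** Four places address weekly doses above 50 IU/kg, and each has a different rule: a free clinical judgement (3.1.1), no route at all (synopsis), sponsor approval (3.2.1.4), or a trough threshold combined with a bleeding need (footnote 2). Nothing says which takes precedence for Arm 4.

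This matters because Amendment 6 records that the study is closed for previously treated patients. Arm 4, which enrols males up to 18 years of age, is the arm these passages still govern. Two sites could give a child the same weekly dose, one asking for approval and the other not, and both could cite the protocol. What is at stake is whether the sponsor's approval step operates as intended, and whether such doses are recorded as deviations in a consistent way.

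**Working it through.** The 50 and 250 IU/kg limits are set values, not derived ones, so there is no planned figure to reproduce. The check is a conversion to 28 days, followed by a comparison of the passages.

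**Inputs.** Interval 7 days (3.2.1.1); upper dose 75 IU/kg (3.1.1, Arm 4); per-injection maximum 50 IU/kg (synopsis, 3.2.1.4, Table 1); 28-day limit 250 IU/kg (3.2.1.4).

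**Formula.** 28-day total = (28 / interval) × dose per injection.

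- Weekly doses in 28 days: 28 / 7 = 4.
- At 75 IU/kg: 4 × 75 = 300 IU/kg. Excess over the limit: 300 − 250 = 50 IU/kg, and 300 / 250 − 1 = 20%.
- Per injection: 75 / 50 − 1 = 50% above the 7-day maximum.
- At 50 IU/kg: 4 × 50 = 200 IU/kg, inside the limit.
- Weekly dose that just reaches the limit: 250 / 4 = 62.5 IU/kg.

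**Do the other Table 1 maxima respect the limit?**

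- 10-day, 75 IU/kg: 2.8 × 75 = 210, or 3 × 75 = 225 if three doses fall in the window.
- 14-day, 75 IU/kg: 2 × 75 = 150.
- 21-day, 100 IU/kg: 28 / 21 × 100 = 133, or 2 × 100 = 200 if two doses fall in the window.

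All stay below 250. Only the Arm 4 upper figure, taken weekly, goes past it.

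**How each passage treats a weekly Arm 4 dose held for 28 days**

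| Passage | Above 50, up to 62.5 IU/kg | Above 62.5, up to 75 IU/kg |
|---|---|---|
| 3.1.1, Arm 4 | Allowed | Allowed |
| Synopsis | Over the maximum | Over the maximum |
| 3.2.1.4 | Needs approval (per injection) | Needs approval (per injection and 28-day) |
| Table 1 footnote 2 | Acceptable if the trough condition is met | Per-injection condition only; does not lift the 28-day limit |

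**Section 3.1.2.** Section 6.2.1 gives a dose formula and target FIX levels but no 35 to 75 IU/kg range, so the pointer does not settle the scope. If the sentence covers Arm 4, its lower end of 35 differs from the 25 in Section 3.1.1. If it covers Arms 1 to 3 across the 7-, 10- and 14-day intervals, its lower end differs from the 25 that Table 1 suggests for the 7-day interval. The same 35 to 75 range appears in Section 3.2.2, but there it is for on-demand treatment.

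**The case against.** The strongest reply is that the body sections can be read together. Section 3.1.1 gives a starting range and an outer bound, footnote 2 gives a clinical condition for exceeding 50 IU/kg, and Section 3.2.1.4 supplies approval. Silence about approval in Section 3.1.1 does not waive it, and the 28-day limit is stated for every interval. This stands in part. A reader might infer that the protocol forbids 75 IU/kg weekly outright. It does not, because both limits in Section 3.2.1.4 give way to approval. The cumulative reading is nevertheless not written down: the Arm 4 text lacks the cross-reference that the Arm 1 text has, footnote 2 does not say whether approval is also needed, and the synopsis admits no exception.

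Second, the Arm 4 paragraph also covers on-demand and prevention dosing, and the on-demand maximum is 75 IU/kg. The upper figure might therefore belong to on-demand use. That cannot be excluded. Against it, the section heading is routine prophylaxis, and 25 to 50 IU/kg is the 7-day prophylaxis range in Table 1, whereas on-demand is 35 to 75 and prevention 35 to 50. If on-demand was meant, the text needs to say so.

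Third, the synopsis is a condensed summary, and the same paragraph refers to a lead-in dose that an untreated child cannot have. That is fair, and it makes the synopsis an alignment matter. It still gives a reader a flat maximum.

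Fourth, a reader might infer that 35 to 75 IU/kg is a further Arm 4 range, so that 25 against 35 is an established conflict. The link rests on sentence position alone; only the unclear scope is established.

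Finally, a reader might infer that the dose and consumption results would be distorted. The SAP does not support this. Section 4.8 summarizes assigned and received doses, Section 4.11 uses recorded units and weight, Section 4.10 measures dose compliance against the prescribed dose, and Section 3.6.5 uses no per-protocol set for PUPs. Only the deviation tabulation in Section 4.5 depends on which rule is applied.

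**Conclusion.** The point holds as an internal inconsistency about the conditions for weekly Arm 4 doses above 50 IU/kg. It is not an arithmetic error, and it is not an absolute contradiction with the 28-day limit.

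The affected range is above 50 and up to 75 IU/kg weekly. Above 62.5 IU/kg sustained weekly, the 28-day limit is engaged as well, reaching 300 against 250 IU/kg at the top. These figures assume that the 75 IU/kg bound applies to prophylaxis and that all four doses in the window are at the stated level. With two doses at 75 and two at 50, the total is 250, exactly at the limit.

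The consequence is uncertainty over when a child's dose needs sponsor approval and when it counts as a deviation. The documents do not show that any patient was harmed or that any summary would be computed differently. Correction is worthwhile because the affected arm is the one still open.

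**What to change.** Reconcile the synopsis, Sections 3.1.1, 3.1.2 and 3.2.1.4, and Table 1 with its footnote 2. In one place, state for Arm 4:

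- the prophylaxis range, the per-injection maximum and the 28-day limit that apply;
- whether exceeding them needs sponsor approval, a trough condition, or both;
- whether the 75 IU/kg in Section 3.1.1 refers to prophylaxis or to on-demand dosing.

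Say which arms and intervals the 35 to 75 IU/kg sentence in Section 3.1.2 covers, and correct its pointer to Section 6.2.1. Then have the other passages refer to that single statement. Which values and conditions belong there is for the sponsor's clinical team; none is proposed here.

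The cost is protocol wording. Because the wording bears on subject safety, Section 14.3 suggests an amendment with IRB/IEC approval and not an administrative change. No SAP method has to change, but the rule used to classify weekly doses above 50 IU/kg already given should be documented before the Section 4.5 deviation tables are produced.
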